6.3. Visit 3 (Day 5)

After about 96 hours (Day 5), the participant will return for a final assessment.

This assessment time is the final (reference criterion) assessment as it is necessary to allow for up to five days for a skin reaction to appear.

At the visit, the medical professional with training in patch testing will review the skin for any reaction and document in the CRF.

A complete set of photos will be taken to document the reactions using the smart phone application and other camera systems.

Participant feedback on the patch testing experience will be documented.

Severe contact dermatitis will be treated with topical steroids if needed.

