3.1. General Description

The overall adaptive study is designed to include three consecutive phases. Prior to the start of the adaptive study, a pilot cohort of up to 10 participants are planned to optimize the study protocol logistics, including camera usage, image capture parameters and documentation, and lighting conditions. This pilot phase is to ensure that the data captured during the adaptive study are as optimal as possible based on all study procedures. Pilot subjects will undergo the same overall protocol scheme shown below and receive remuneration. The data collected will be used to refine the protocol, with amendments as necessary.

Each of the phases in the adaptive study is intended to advance the technologies and evaluate how scalable the technologies will be outside the clinical practice. The phases described below cover the primary intended workflow using the Mayo Clinic owned iPhone. Additional protocol actions including additional photography and ascertainment of other clinical study data (including adverse events) will occur to enrich the study data.

Common study flow for all phases of the study:

On day 1 a routine skin examination will be conducted. This will include photographic documentation of the condition of the skin region to be tested. Afterwards, the test patches will be applied to commence the testing. On day 3, the patients will return to remove the patch tests and document the test sites using the study iPhone app and the additional camera setups as specified in the protocol. On day 5, the final photographic documentation will be acquired and the final clinical assessment for allergic contact dermatitis will be provided by a medical professional with training in patch testing to establish the reference criterion.

Specific adaptation according to each phase of the study:

Phase 0 (n <=10): This pilot phase will study up to 10 participants to optimize the study manual of operations, ensuring the logistics and timing of all study visits to optimally conduct the three main phases of the study.

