Phase 1 (n=100): Phase 1 initiates where the prior pragmatic clinical trial (NCT053339750, IRB 21-011596) concluded. This phase of the study will advance the technology in material ways through shifting day 3 (patch removal) and day 5 (final photographic documentation of test site) to the participant in the study. Participants will be guided in the use of the application and primary iOS/iPhone photographic documentation; the study team will provide additional photographic documentation and review of the test site to establish the reference criterion.

Phase 2 (n=25): For phase 2, the patch will be placed on the inside of the arm by the participant. The study documentation will proceed identical to Phase 1.

Quality Checkpoint Decision: Patch able to be successfully applied by patient in >90% of the cases (fewer than 3 placement errors).

Phase 3 (n=25): In phase 3, the entire study will be patient-led, although on-campus visits will be required to obtain the allergen panel and evaluate the reference criterion. This phase will use a prototype novel test kit with printed instructions and necessary supplies to clean the arm, assemble the patch application jig, install the app, and perform the patch testing. Human observation and patient surveys will be conducted to evaluate the human factors aspects of the test kit.

For both Phases 2 and 3, participants will be invited to complete the Patient Journey questionnaire at least a week ahead of the scheduled visit 1 appointment by email. Responses will be summarized to suggest allergens that would be recommended based on past exposures. The recommendations will be constrained to only the set of allergens tested in this protocol (See Section 5.2). Participant will have the option to select the standard allergens used in Phase 1 of the study or use up to 10 of the recommended allergens based on the Patient Journey.

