3.4. Identification of Source Data

Study-specific case report forms (CRFs) will be used to document all of the following:

1. Demographics and medical history including assessment of Fitzpatrick skin types
2. Patient will be assigned to one of the randomized allergen templates that will be used for the study.
3. Documentation of the randomized location of the allergens on the test patch used with the participant
4. Documentation of the reference criterion (in person assessment by medical professional with training in patch testing Day 5) as well as the initial impression of reactions at Day 3 immediately following the removal of the patches.
5. Participant feedback on the user experience of the test patching
6. Documentation of the blinded human review of the photographs acquired on Day 3 and Day 5
7. Adverse events

The following source data will not be directly collected in the CRFs, but will be integrated into the master database:

- Test site photographs
- AI predictions on the photographs

4. Subject Selection Enrollment and Withdrawal

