6.2. Visit 2 (Day 3)

Participant will be asked to return after 48 hours (Day 3) for patch removal and preliminary reaction assessment.

Skin will be assessed and documented for reactions which may include irritation, redness, and/or swelling localized to the patch test area.

The reaction will be documented as negative, irritation, or positive contact allergic reaction using the scale described below in section 6.6.

Participant will be encouraged to let the study team know if there was any itching or burning while the patches were in place.

A complete set of photos will be taken to document any reactions with the smart phone application and other camera systems.

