6.7. Participant Remuneration

Participants will be remunerated \$125 / visit (\$375 total for completing the study).

Schedule of Events						
Study Activity	Day 1	Day 2	Day 3	Day 4	Day 5	Off Study Evaluation
Informed consent	X					
History ^a	X					
Concurrent meds	X					
Limited physical exam ^b	X					
Patch placement ^c	X					
Documentation of allergen location	X					
Photographic Documentation ^c	X		X		X ^d	
Patch Removal			X			
Reaction Assessment			X		X	
Participant feedback					X	
Adverse Event Assessment			X		X	X

- a. Demographic information, medical history
- b. Fitzpatrick skin type assessment, arm inspection
- c. Photographic documentation of volar aspect of forearm (primary and optional secondary test sites) taken with the approved photographic assessment
- d. In person assessment on Day 5 used as reference criterion
- e. Phase 1 & 2 will be done by provider. Phase 3 done by patient.

7. Statistical Plan

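### The order of app photography and in-person reading is inconsistent, and nothing keeps those who take or guide the primary app images from knowing the reference result

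*Combined protocol and SAP*

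**What the plan says.** Four places in the combined protocol and SAP bear on the order of the two steps.

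- **Section 6.3 (Day 5)** lists the reference reading first: "At the visit, the medical professional with training in patch testing will review the skin for any reaction and document in the CRF". The photographs come next: "A complete set of photos will be taken to document the reactions using the smart phone application and other camera systems".
- **Section 6.2 (Day 3)** has the same order. The grading comes first ("The reaction will be documented as negative, irritation, or positive contact allergic reaction using the scale described below in section 6.6"), and the photographs are the last item ("A complete set of photos will be taken to document any reactions with the smart phone application and other camera systems"). Section 3.4 places the Day 3 grading close to patch removal: "the initial impression of reactions at Day 3 immediately following the removal of the patches".
- **Section 3.1 (common study flow)** has the opposite order for Day 5: "On day 5, the final photographic documentation will be acquired and the final clinical assessment for allergic contact dermatitis will be provided".
- **The Schedule of Events** (after section 6.7) places the row "Photographic Documentation" above the row for reaction assessment.

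On who takes the images, section 3.1 says of Phase 1: "Participants will be guided in the use of the application and primary iOS/iPhone photographic documentation". It gives the additional photography and the reference review to the study team, without separating the staff. Section 5.6 masks the reader of the photographs and delays that reading by at least one month. It does not mention the participant or the staff who guide capture. Section 8.4 lets the in-person evaluator see allergen identities after a reaction and has the cause told to the participant, without saying when. No section gives a rule on retaking or choosing app images.

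**The concern.** The app images are what both the AI and the photograph reader judge (section 7.2.2), and the in-person Day 5 reading is the reference. In a diagnostic accuracy study the index material should be collected without knowledge of the reference result. If the reading comes first, whoever holds or guides the phone may know which sites were called positive. A frame might then be retaken, refocused or chosen until the known reaction shows well. The skin has also been examined by then.

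What is at stake is absolute performance against the in-person reading: the primary objective (section 2.1) and the wish in section 7.2.2 that both readers exceed 95% accuracy. The Study Summary gives the aim as support for fully remote testing. No expert reads the skin first in that setting, so images taken after a reading may represent it less well. Images already taken cannot be repaired at the analysis stage.

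**Working it through.** The plan gives no figure for this effect, so there is none to reproduce. The check has two parts.

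**1. Order and safeguards, side by side**

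| Place | Listed first | Listed second |
|---|---|---|
| 6.2, Day 3 | grading | photographs |
| 6.3, Day 5 | reference reading | photographs |
| 3.1, Day 5 | photographs | reference reading |
| Schedule of Events (rows) | photographs | reaction assessment |

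None of the four uses a word such as *then* or *after* between the two steps. The order is therefore not fixed, and the places point in different directions.

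For each party, could the result be known at capture if 6.3 is followed as listed?

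- Photograph reader: no, masked by 5.6.
- AI: no, run asynchronously on stored images (1.2).
- Staff guiding the participant: not masked; their role in the reading is not stated.
- Participant, who takes the primary image in Phase 1: not masked, and may have been told the cause of a reaction (8.4).

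**2. What a given number of affected sites would mean**

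Inputs: 100 Phase 1 participants (3.1); 10 primary allergens each (5.2.1); 15% positive sites expected (7.1); 6.4% positive in the prior trial with this panel, 132/2,060 (1.3.2). The number of affected sites, five, is my assumption. The documents give no basis for it.

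- Sites: 100 × 10 = 1,000.
- Positive sites: 0.064 × 1,000 = 64, to 0.15 × 1,000 = 150.
- One positive site changed from missed to detected moves sensitivity by 1/150 = 0.67 points, to 1/64 = 1.56 points.
- Five such sites move sensitivity by 5/150 = 3.3 points, to 5/64 = 7.8 points.
- The same five sites move accuracy by 5/1,000 = 0.5 points.

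For the AI-minus-human accuracy difference, the shift is (sites gained by the AI − sites gained by the human reader)/1,000. If both gain the same number it is zero. If the AI alone gains all five it is 0.5 points, against a margin of 5 points.

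On scope to target single sites: in the prior trial 2,060 sites came from 206 images, and 2,060/206 = 10 sites per image. If the present app works the same way, one frame covers the whole panel.

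**The case against.** The strongest reply is that 6.2 and 6.3 are lists, not sequences. Where section 3.1 means a sequence it says so: on Day 1 the photographs come first and the patches are applied afterwards. Row order in the Schedule of Events is no guide either, since it places patch placement above photography and photography above patch removal. The one sentence that names both Day 5 steps puts photographs first. The within-visit order may also be settled in the operations manual, which Phase 0 is meant to refine and which is not among the documents. This stands as far as it goes: the protocol does not prescribe reading first. It does not prescribe photographs first either.

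Second, capture is controlled. The app automates it (1.2), and a cradle and light-blocking shell standardise distance and lighting (6.4). Whole-panel frames would make it hard to favour one site. Reactions are visible to anyone at the arm, and by Day 5 the Day 3 impression is already on record. So photographing first removes only part of the knowledge. All of this limits the size. It does not govern retakes or the choice of frame.

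Third, a reader might infer that the images are not independent of the reference and that performance is therefore inflated by 3 to 8 points. The documents do not support that. No passage describes a targeted retake or says that the guide made or saw the reading. The 3 to 8 points rest on an assumed count of five and concern sensitivity, which is secondary. On the primary endpoint, accuracy, the same count gives 0.5 points. Nor can one infer that the non-inferiority test is materially biased, because both readers use the same app images.

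**Conclusion.** The point holds as an inconsistency with an unprotected step, not as a demonstrated bias. Sections 6.2 and 6.3 disagree with section 3.1 and the Schedule of Events on which step is listed first, and masking stops at the photograph reader. Followed as 6.3 is listed, the plan lets the participant and guiding staff know the reference result at capture.

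Any effect would probably favour absolute sensitivity and accuracy, and would largely cancel in the AI-versus-human contrast. Its size cannot be estimated. The figures above illustrate scale only, and assume 1,000 evaluable Phase 1 sites, 64 to 150 positives and five affected sites. The change is still worth making before enrolment: it costs little, suits the remote-use aim, and cannot be made after the images exist.

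**What to change.** 1. Amend 6.3 to agree with 3.1. At Day 5 the participant's app image set is captured, checked for technical quality and locked before the in-person reading is made, recorded or communicated.
2. Amend 6.2 likewise. At Day 3 the app images are taken right after patch removal and the impression is recorded next, so that section 3.4 is still met.
3. Allow technical retakes only before the reading. Flag any app image taken afterwards and use it only in a sensitivity analysis.
4. Let the other camera systems follow the reading.

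Cost: a small change in visit flow and one flag in the database. A few more sites may count as incorrect under the worst-case rule in section 7.3.2 if a locked image proves unusable; the quality check before locking should keep these few. Some knowledge will remain, because reactions can be seen by whoever is present.

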6.4. Photographic Documentation

At each study visit with photographs taken, a comprehensive set of images will be captured. This will include the primary acquisition using the study's smartphone application but also novel imaging including:

Full spectrum analysis:

1. Unfiltered (clear)
2. Filtered to specific wavelengths: 590nm, 665nm, 720nm, and 850nm
3. Additional (wide range) filters: Blue IR (excluding visible light spectrum, except blue, and including infrared) and Hot Mirror (~100nm – 700nm; i.e., visible light)

4. Lighting conditions – routine clinical lighting, exposed with a Wood's Lamp ("black light"), exposed with

Live video clips: Short videos using the iPhone's live capture

Photogrammetry: A series of 20 or more images of each test site will be captured from all angles. These images are reconstructed using software to form a three-dimensional rendering of the test site.

Tripod / camera assist device: The smartphone will be supported with a phone cradle during the photographic documentation. This device includes a shell to block ambient light while allowing for the phone to be securely supported during the documentation process. This device is to standardize the distance and lighting while removing artifacts from the background of the image that could be identifiable data.

6.5. Off study evaluation (post reaction care, if applicable)

In the event of a positive allergic reaction that should be treated with topical steroids, the participant will be provided over-the-counter hydrocortisone. If prescription strength steroids are required, a prescription will be made.

6.6. Reaction Grading Scale

Reactions will be graded as negative, irritant, or positive. Positive reactions will be rated as doubtful (1), weak (2), strong (3), or extreme (4) depending on their physical appearance. Doubtful reactions only have faint erythema, weak reactions are those with non-vesicular erythema, strong reactions are raised and have vesicular or non-vesicular erythema, extreme reactions are bullous or ulcerative in nature.

(Spiewak et al)

Symbol	Morphology	Assessment
-	No reaction	Negative reaction
?+	Faint erythema only	Doubtful reaction
+	Erythema, infiltration, possibly papules	Weak positive reaction
++	Erythema, infiltration, papules, vesicles	Strong positive reaction
+++	Intense erythema, infiltrate, coalescing vesicles	Extreme positive reaction
IR	Various morphologies, e.g. soap effect, bulla, necrosis	Irritant reaction

(Johansen et al)

6.7. Participant Remuneration

Participants will be remunerated \$125 / visit (\$375 total for completing the study).

Schedule of Events						
Study Activity	Day 1	Day 2	Day 3	Day 4	Day 5	Off Study Evaluation
Informed consent	X					
History ^a	X					
Concurrent meds	X					
Limited physical exam ^b	X					
Patch placement ^c	X					
Documentation of allergen location	X					
Photographic Documentation ^c	X		X		X ^d	
Patch Removal			X			
Reaction Assessment			X		X	
Participant feedback					X	
Adverse Event Assessment			X		X	X

- a. Demographic information, medical history
- b. Fitzpatrick skin type assessment, arm inspection
- c. Photographic documentation of volar aspect of forearm (primary and optional secondary test sites) taken with the approved photographic assessment
- d. In person assessment on Day 5 used as reference criterion
- e. Phase 1 & 2 will be done by provider. Phase 3 done by patient.

7. Statistical Plan

7.1. Sample Size Determination

The primary sample size is determined based on Phase I of the study. With an expectation that 15% of the test sites will be positive, based on the selection of allergens with the highest incidence of reactions, and a target sensitivity of 95%, 90% power, and a minimum clinically relevant difference of 5 percentage points, a total of 130 positive test sites needs to be present in the study to achieve the design specifications. Given the assumption that most participants will only exhibit 1 to 2 reactions and the intraclass correlation of detections remains unknown, the design effect (or variance inflation effect) is not applied to account for potential clustering of reactions per participant. Therefore, with the assumption that each participant will have 1.5 positive reactions on average, we anticipate a requirement for 100 participants.

The sample sizes for Phase II and III have been administratively set based on feasibility of recruitment and testing.

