1.3.2. Study #2: Prospective Clinical Trial (IRB 21-011596)

A prospective, pragmatic clinical trial was designed to advance the technologies associated with a democratized skin patch testing approach that leveraged novel patch designs and an integrated smartphone-based application to capture and upload photographs of the patch testing sites to the cloud. The study incorporated an in person, clinical assessment at all three study visits to establish the reference criterion according to current clinical protocol. Photographs were captured at each visit to provide means to evaluate a novel deep learning model for the detection of allergic contact dermatitis. While the deep learning algorithm's performance could be established relative to the in-clinic reference reading, it was unknown just how well a human reader could function when only exposed to the photographs of the test sites (i.e., not able to palpate suspicious regions). To address this, the study incorporated a human reading protocol where the same photographs, void of any data collected about the patient or information obtained during the clinical visit, were reviewed by humans to determine what the accuracy of the machine learning approach in the context of human readers.

A total of 232 participants consented to participate and 206 reached the day five assessment. A specific purpose of this study was to enroll 50% of participants with Fitzpatrick Skin Types IV – VI. This objective was achieved as the distribution of skin types over the six types were as follows: 46.6% were classified as types IV-VI. The mean (SD) participant age was 39.1 (13.5) years, and 66% (136/206) of the participants were female. A total of 32.0% (66/206) of participants self-identified as being Black or African American, 16.5% (34/206) as Asian (34/206), and 40.3% as White (83/206). A total of 23 participants self-identified as Other (11.2%) or of Hispanic origin (73.9%, 17/23).

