The overall incidence of allergic contact dermatitis in the sample was 6.4% (132/2,060) using the panel of allergens to be tested in the present study. The 206 images yielded 2060 test sites that were expertly evaluated during the in clinic (Day 5) evaluation. The only input to the neural network was the cropped image of the patch test site sites. The CNN model diagnosed the presence or absence of reaction with an AUROC of 0.861 (95% CI, 0.824 – 0.897). Using the previously selected cutoff of 4.88%, this generated an accuracy of 91.0% (95% CI, 89.7%-92.2%), a sensitivity of 58.3% (95% CI, 49.4%-66.8%), and a specificity of 93.3% (95% CI, 92.0%-94.3%).

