4.3. Subject Recruitment, Enrollment and Screening

The recruitment for this study will include participants from Mayo Clinic Florida patients and staff, and collaboration with the University of North Florida.

In 2019, approximately 284 patients had skin patch tests performed at Mayo Clinic Department of Dermatology in Jacksonville Florida. Among these patients, 17 were identified Black or African American with a Fitzpatrick score of 5-6, and 32 were identified as Hispanic or Latino with a Fitzpatrick score of 3-6.

Additionally, we will advertise for a healthy control group throughout Mayo Clinic Florida campus as well as the University of North Florida. In 2019, the University of North Florida student population enrollment was reported at approximately 17,117 students. The distribution of population for minority population of interest is 10% (1,684) Black or African American, 13.3% (2,280) Hispanic or Latino, and 5% (853) two or more races. Potential participants can contact the study coordinator listed in the flyer and/or electronic display to further inquire on eligibility criteria and study questions.

Thus, we estimate that from a pool of 49 eligible patients in Mayo Clinic Florida per year, the robust minority population of employees at Mayo Clinic and student population at University of North Florida, we can achieve full enrollment.

We will monitor enrollment bi-weekly and will hold calls with the study team to clarify questions about eligibility and ensure robust recruitment. If recruitment falls short of numerically defined targets, we will assess reasons for slow accrual and adjust the protocol accordingly.

Patients who have undergone previous patch testing will be screened by an experienced study coordinator for participants with a Fitzpatrick skin types 4 through 6 and eligibility criteria. This study coordinator will call the patient to discuss the study, eligibility, and study logistics, and then will plan to meet the patient at their next visit to the clinic to review and sign the consent (if the patient wishes to participate and is eligible).

Potential participants who answer the advertisement will have a call scheduled with the study coordinator to discuss the study, eligibility, and study logistics. Based on the potential participant's agreement, the study coordinator will schedule a research visit, as well coordinate with the Dermatology medical assistants to schedule the patch testing procedures.

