5.2. Investigational allergens

5.2.1. Primary Test Site (arm 1)

The following ten allergens manufactured by AllergEAZE will be used for patch testing during the study. Potential adverse reactions include pruritus, irritation, skin discoloration, erythema, induration, blistering and ulceration. Pruritus can be managed over-the-counter antihistamines.

While most reactions self-resolve, more severe skin reactions would be managed with topical steroids.

1. Nickel sulfate hexahydrate, 2.5% (18.3%)
2. M. Pereirae resin, 25% / Balsam of Peru (9.2%)
3. Neomycin sulfate, 20% (7.8%)
4. Fragrance mix, 8% (6.7%)
5. Bacitracin, 20% (6.4%)
6. Carba mix, 3% (5.8%)
7. Quaternium-15, 1% (4.4%)
8. Benzoic acid, 5% (3.7%)
9. Propolis, 10% (3.5%)
10. Thiuram mix, 1% (2.8%)

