5.6. Masking/Blinding of Study

The medical professional that reads the photographs of the test sites will be blinded to all clinical information including, but not limited to, the allergen's randomized locations, the in-person assessment of the reactions, and any AI predictions on the images. Effectively, the human read of the photograph will only have the photograph available to form all impressions about the reactions.

The reading of the human interpretation of the photographs will occur at least 1 month after the clinical visit to maintain blinding and washout in the event study staff provide a visual impression of the reaction sites via photographic review.

6. Study Procedures

6.1. Prior to Visit 1 and after study consent, the participant will have an opportunity to complete the Patient Journey. For Phases II and III of the study, this patient journey will be distributed to the patient prior to Visit 1 to allow for the data to be summarized. The summarization will include qualitative and quantitative approaches to quantify the self-reported employment profiles, ancestry, and known allergens to identify which allergens that may be more allergenic to the participant.

Visit 1 (Day 1)

Informed consent will be obtained as well as demographic information, medical history, and current medications questionnaire (see Schedule of Events).

A limited physical exam focused on the forearm will be conducted as well as assessment of participant's Fitzpatrick skin type.

A baseline photo will be taken using the smart phone application and the additional camera systems including the full spectrum documentation and photogrammetry acquisition.

A member of the study team will place the primary test patch on the volar aspect of participants' forearm. The patch contains allergens placed in dime-sized wells. The location of the allergens within the patch will be randomized between participants. The study team member will document the location of each allergen.

The smaller, 4 well patch, on the secondary arm will be placed similar manner to the primary test patch.

Tape or waterproof dressing may be used to secure the patch strips. Participant will be given instructions to avoid water contact with patch, and avoidance of sun exposure.

Participants will be allowed to take over the counter histamine blockers to alleviate pruritus.

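### Section 7.1 plans on 1.5 positive sites per participant, but the prior trial with the same panel gave 0.64, so 100 Phase 1 participants should yield about 64 positive sites, not 130

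*Combined protocol and SAP*

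**What the plan says.** Section 7.1 bases the sample size on Phase 1. Its inputs are a 15% positive rate ("With an expectation that 15% of the test sites will be positive, based on the selection of allergens with the highest incidence of reactions"), a target sensitivity of 95%, 90% power and a 5-percentage-point difference. From these it states that "a total of 130 positive test sites needs to be present in the study to achieve the design specifications". It applies no design effect and concludes that "with the assumption that each participant will have 1.5 positive reactions on average, we anticipate a requirement for 100 participants".

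Section 1.3.2 describes the prior prospective trial that Phase 1 continues from (section 3.1). The incidence there "was 6.4% (132/2,060) using the panel of allergens to be tested in the present study", from 206 images with ten sites each. On retention it says: "A total of 232 participants consented to participate and 206 reached the day five assessment".

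The primary patch has ten sites (section 5.2.1: "The following ten allergens manufactured by AllergEAZE will be used for patch testing during the study"). A second patch goes on the other arm (section 6, Visit 1: "The smaller, 4 well patch, on the secondary arm will be placed similar manner to the primary test patch").

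Sections 6.6 and 7.2.1 count a doubtful reaction (grade 1) as positive. Section 7.2 makes accuracy over all sites the primary endpoint, with a 5-point non-inferiority margin for AI against human readers, and lists sensitivity as secondary. Section 7.3.3 sets alpha at 0.05.

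**The concern.** The planning rate is more than twice the rate the protocol itself reports for the same panel. The only reason 7.1 gives for 15% is the choice of high-incidence allergens, but the 6.4% was observed with that choice already made. The stated reason therefore cannot explain the difference.

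The 130-site count is the only justification in 7.1 for 100 participants. If the yield is about half of that, sensitivity will be estimated much less precisely than the 90%-power statement implies. A reader may also take that 90% to cover the primary non-inferiority test, although the visible text of 7.1 ties it to sensitivity and gives no power for the accuracy comparison.

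**Working it through.** **Inputs.** 15%, 1.5 per participant, 130 sites, 100 participants, 95% sensitivity, 90% power, 5 points (7.1); 132/2,060 sites, 206 of 232 retained (1.3.2); ten primary sites (5.2.1); alpha 0.05 (7.3.3).

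**The plan's own chain**
- 15% × 10 sites = 1.5 per participant, so 7.1 is counting the primary patch only.
- 130 / 1.5 = 86.7, so 87 participants; 100 leaves about 13% slack (100 × 1.5 = 150 sites).
- These steps are internally consistent. The problem is the 15%.

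**Yield at the documented rate**
- 132 / 2,060 = 6.41%; 132 / 206 = 0.641 per participant.
- 100 × 0.641 = 64 positive sites, 49% of 130.
- With retention 206 / 232 = 0.888 (an assumption for this trial): 64 × 0.888 = 57, 44% of 130.
- Participants needed for 130: 130 / 0.641 = 203.
- Rate needed for 130 of 1,000 sites: 13.0%, or 2.03 × 6.41%. With 888 sites retained: 14.6%.

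**Sampling error in the prior rate**
- Exact 95% CI for 132/2,060: 5.39–7.55%, or 54–76 per 1,000 sites, treating sites as independent.
- Largest design effect for ten sites: 1 + 9 × 1 = 10. Effective n = 206; CI 3.5–10.7%, or 35–107 per 1,000, still below 130.

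**Would the second patch close the gap?** Assume that the unlabelled percentages in 5.2.1 are reaction rates and that allergens react independently. Leave out the methylchloroisothiazolinone / methylisothiazolinone well, for which no rate is given.
- Combination #1: 0.183 + 0.190 + 0.167 + 0.118 = 0.66 per participant.
- Combination #2: 0.183 + 0.092 + 0.067 = 0.34.
- Mean 0.50, so about 50 per 100 participants.
- Added to 64 (or to 69, since the 5.2.1 percentages sum to 68.6%): 114–119 before attrition, below 130.

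**Precision for sensitivity (exact 95% CI, before clustering)**

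| Positive sites | Detected | 95% CI |
|---|---|---|
| 130 | 124 | 90.2–98.3% |
| 130 | 123 | 89.2–97.8% |
| 64 | 61 | 86.9–99.0% |
| 57 | 54 | 85.4–98.9% |

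**Reproducing the 130.** One-sample normal approximation, 95% against 90%, 90% power:
- Variance at 95% throughout, n = 0.95 × 0.05 × (z_α + z_β)² / 0.05²: 163 (one-sided 0.05) or 200 (one-sided 0.025).
- Variance at 90% under the null and 95% under the alternative, n = (z_α√0.09 + z_β√0.0475)² / 0.05²: 239 or 301.
- Paired comparison, n = ψ(z_α + z_β)² / 0.05²: 130 requires reader discordance ψ of 3.1% (one-sided 0.025) to 3.8% (one-sided 0.05).

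Section 7.1 names no test and states no discordance, so the 130 cannot be reproduced from its stated inputs. The shortfall does not depend on this; it takes 130 as given.

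**The case against.** The best defence is that the two rates may not measure the same thing. Section 1.3.2 reports incidence of allergic contact dermatitis and does not say whether doubtful reactions are among the 132; here they count as positive. Recruitment may also differ: section 4.3 says "Patients who have undergone previous patch testing will be screened by an experienced study coordinator", although it also advertises for healthy controls, so the direction of any shift is unclear. The intervals above cover sampling error only, not a change of definition or population, and so do not bound the yield. All of this stands. But the rate would have to double, and 7.1 offers neither reason.

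The retention factor is also soft. It runs from consent to Day 5, and the documents do not say how many of the 26 losses came before patch placement. The 57 is therefore conditional; the 64 is not affected.

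On the 130, a paired formula can reach it, and AI and human readers do assess the same sites. The fair statement is that the test and its inputs are missing, not that 130 is impossible.

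Finally, sensitivity is secondary, and the primary accuracy analysis has about 1,000 Phase 1 sites whatever the positive rate. That limits the consequence. It does not rescue a sample-size rationale that the protocol's own data contradict.

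**Conclusion.** The concern holds. At the only rate the protocol documents for this panel, Phase 1 should yield about 64 positive primary-patch sites (57 with the prior trial's retention) against the 130 that 7.1 requires. This rests on the prior trial's positive rate carrying over. A higher rate is possible if doubtful reactions were left out before or if recruitment differs, but reaching 130 needs 13.0% and no evidence for that is given.

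The effect is on the sensitivity estimate and on the stated justification for 100 participants. A loss of power for the primary accuracy test is not shown. The visible text gives no power for that test; a figure after 7.2.1 could not be seen. The correction is needed because 7.1 claims a yield and a power that the plan's own data do not support.

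**What to change.** In section 7.1:

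1. Base the expected yield on 6.4% (0.64 per participant) and state about 64 positive primary-patch sites in Phase 1, or about 57 if 206/232 retention is assumed, labelled as an assumption.
2. If a higher rate is kept because doubtful reactions count or recruitment differs, give the evidence and show the yield as a range from 6.4% upward.
3. Withdraw the statement that 100 participants meet the 130-site, 90%-power specification unless that rate is supported.
4. State the expected precision for sensitivity with an exact or Wilson interval, noting that clustering is not included: for example 61/64, 86.9–99.0%, and 54/57, 85.4–98.9%. An example near the 58.3% AI sensitivity reported in 1.3.2 would be a useful addition: 37/64 gives 44.8–70.1%.
5. If the 130 is kept, give its test, alpha, sidedness and formula, and the discordance if it is paired.
6. Say that this calculation refers to sensitivity and not to the primary accuracy comparison.

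The cost is wording in 7.1 only, with no extra enrolment or procedures. The price is a less favourable stated figure, and 100 participants would then rest on expected precision rather than on a power claim.
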